5.4 VACCINATION

The site for injection cleaned with an alcohol wipe before the injection. The vaccines will be given by intramuscular (IM) injection into the deltoid muscle, excluding the dmLT adjuvant which is given by TCI. Alternating deltoids will be used for subsequent immunizations. A study vaccination outside of a participant's vaccination window may occur at the discretion of the PSRT.

5.5 STUDY VISITS

Participants will have up to 26 clinic visits. The active study phase will last a total of 105 weeks, which will include the time of the first screening visit through the final clinic study visit. In addition, participants will be contacted once per week for 3 weeks (3 phone contacts) following the 105 week active study phase. At these contacts, staff will collect the information listed below.

- Confirmation of vital status; if deceased, attempt to learn cause and date of death;
- If participant is alive, record the participant's responses to questions regarding any occurrence of the following events since the last study contact:
 - Life-threatening adverse experiences;
 - Persistent or significant disability/incapacity;
 - Hospitalizations and reasons;
 - New diagnosis of HIV infection; and
 - Pregnancies and outcomes, including congenital anomalies/birth defects

All such events will be recorded, and adverse events other than HIV infection will be assessed for relationship to study product(s). Clinic visits will only be required if HIV confirmatory testing is necessary; however, a clinic visit may be arranged for other reasons.

Evaluation of the safety of the study vaccines is outlined in the schedule of evaluations (SOE) and will include laboratory studies, medical history, physical assessment by clinicians, and participant self-assessment recorded on a 7-day diary card. Additional study visits may be required if, in the investigator's opinion, any lab value warrants repeating. The first vaccination visit could take up to 6 hours, but the other vaccination visits take about 4 hours each. Most other follow-up clinic visits will usually take about 2 hours.

Total blood volume drawn from each participant will not exceed the US Department of Defense (DoD), American Association of Blood Banks (AABB) and FDA guidelines of 450 mL in an eight-week period. If a participant is anemic, each visit's blood volume will be reviewed, and the blood drawn for research may be reduced or not drawn at all, depending on the severity of anemia.

Table 4: Visit Procedures

Clinic visit activities
Screening Visit 
 • Study briefing and collection of contact information • Informed consents • Test of understanding • Review medical history including medications • Vital signs (blood pressure, pulse, respiratory rate, and oral temperature) • Complete physical exam including height and weight • CBC, creatinine, ALT, and AST • HIV risk counseling • HIV test with counseling before and after • Hepatitis B and C • Syphilis test • Pregnancy counseling • Urine pregnancy test for women • Urinalysis (dipstick) for blood, protein, and glucose
Optional 
 • Pap smear for women who agree to cervicovaginal secretion collection
Vaccination Visits 
 • Targeted physical exam and review of current medication • Vital signs (blood pressure, pulse, respiratory rate, and oral temperature) • Review eligibility • HIV risk counseling • Blood draw for safety*, research and HIV tests • Pregnancy counseling • Urine pregnancy test for women • Enrollment and randomize* • Administer vaccination or placebo • Post-injection observation for 30-60 minutes • Adverse event documentation • Provide a diary card and instruction
Optional 
 • Mucosal secretion collection*

Phone/Clinic Follow Up Visits after Each Vaccination and as Needed

- Assessment of wellbeing
- Measure vital signs (blood pressure, pulse, respiratory rate, and oral temperature) *if the participant comes to the clinic*
- Review of symptoms
- Adverse event documentation

Telephone follow-up will be the default method for this visit. Home visits will be done for those participants who will not be reachable by phone.

Follow Up Visits to Include Final Visit

- Targeted physical exam and review of concomitant medication
- Measure vital signs (blood pressure, pulse, respiratory rate, and oral temperature)
- Body weight, if clinically indicated
- HIV risk counseling
- Pregnancy counseling
- Urine pregnancy test for women if mucosal secretion collection or lymph node biopsy*
- Review of diary card*
- Adverse event documentation
- Blood draw for safety, research, and HIV tests*

Optional

- Mucosal secretion collection*
- Lymph node biopsy and biopsy site assessment*

* See Appendix A: Schedule of Evaluations

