4. To evaluate the influence of various adjuvants on cellular immune responses.
5. Describe mucosal humoral responses across vaccination regimens in cervicovaginal and rectal secretions and semen.

Exploratory

1. Characterize B-cell functional specificities for each vaccination regimen.
2. Characterization of innate immunity.
3. Assess the innate/gene expression induced across vaccination regimens (DNA microarray, RNA sequencing) to compare relative influence of various

adjuvants in the gene expression profiles sorted T cell, B cell, and innate cell subsets.

4. Perform systems serology analyses.

Sub-objective

In participants who elect to undergo lymph node biopsy, characterize HIV-specific responses, T cell activation, T follicular helper (Tfh) cell and B cell distribution in intact lymph nodes (excision of intact peripheral inguinal lymph node) at weeks 14 and 58.

Duration of Individual Subject Participation

Each participant will be enrolled for 108 weeks (105 weeks of clinic visits and then contact by phone once weekly for an additional three weeks to inquire about medically attended adverse events).

Estimated Time to Last Subject/Last Visit

Approximately 137 weeks (about 2 years, 8 months)

LAY SUMMARY

The Kenya Medical Research Institute (KEMRI) in collaboration with the U.S. Military HIV Research Program (MHRP) is conducting a study on HIV vaccines. A vaccine is a medical product given to prevent certain diseases, most often infectious diseases. The vaccine may educate the human body to form a defensive response to try to prevent the disease from the beginning or taking hold of the body. This defensive response called the immune response, and it is the body's way to fight infections.

The experimental HIV vaccines tested in this study are Env-C Plasmid DNA and HIV Env gp145 C.6980 protein given with different adjuvants to increase the immune response. An adjuvant is a substance added to vaccines that can help to make the vaccine more effective by improving the immune response or causing the immune response to last longer than without the adjuvant. These adjuvants are mixed with the vaccines and injected into the muscle or placed on top of the skin. The HIV vaccines contain a piece of genetic material or a protein copied from the HIV virus cover (Env), but they do not contain the virus itself. The vaccines cannot cause HIV infection or Acquired Immune Deficiency Syndrome (AIDS).

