RV460 is an exploratory study that will assess the safety, tolerability, and immunogenicity of a vaccine regimen consisting of priming with an Env-C Plasmid DNA vaccine (with or without novel adjuvants) when given with or without adjuvanted HIV Env gp145 C.6980 protein vaccine and boosting with adjuvanted gp145 C.6980 protein with or without the gp120 DNA vaccine. The study will be carried out at the KEMRI/US Army Medical Research Directorate-Africa (USAMRD-A), Clinical Research Centre, Kericho; and 126 healthy adults will be enrolled. Participants enroll randomly into one of seven groups which have 15/3 vaccine/placebo recipients per group. Each participant will receive six injections (prime at week 0, 4, 12; boost at week 20, 32 and 56) followed up for a total of 108 weeks.

Study objectives will be met by the testing of blood samples from all participants. Willing and eligible participants have the option to provide lymph node and mucosal secretion samples (semen, cervicovaginal, rectal), which will provide the data for objectives 2 and the sub-objectives. Exploratory objectives may be met by genetic analysis including but not limited to Human Leukocyte Antigen (HLA) subtyping.

PRECIS

Title

A Randomized, Double-Blind Phase 1 Trial to Evaluate the Safety and Immunogenicity of Priming with Env-C Plasmid DNA Vaccine Alone, with Different Adjuvants, or with an Adjuvanted HIV Env gp145 C.6980 Protein Vaccine and Boosting with the Adjuvanted HIV Env gp145 C.6980 Protein Vaccine with or without the Env-C Plasmid DNA Vaccine in Healthy HIV Uninfected Adults in Kenya

Clinical Phase

Phase 1

Study Duration

Participants are seen in the clinic for 105 weeks following enrollment and randomization. Participants will be contacted by phone once weekly for an additional three weeks to inquire about medically attended adverse events. The total study-related activities may last up to 6 years (2-3 years screening and clinical activities; 2-3 years of laboratory assays and data analyses).

Participants

Healthy, HIV-uninfected male and female volunteers aged 18 to 40 years.

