8.1.6 MEDICALLY ATTENDED ADVERSE EVENTS

The FDA requests that clinical trials of preventive vaccines with adjuvants such as ALF43 and dmLT provide for collection and analysis of data relating to medically attended adverse events (MAAEs) among subjects in all treatment groups through 12 months or longer following the last study vaccination, due to the theoretical potential for induction of autoimmune or auto-inflammatory diseases.

MAAEs are defined as AEs with medically attended visits including hospital, emergency room, urgent care clinic, or other visits to or from medical personnel for any reason. Adverse events (e.g., abnormal vitals) identified at a routine study visit will not be considered MAAEs.

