8.2.1.1 EAE Reporting Requirements for the Study

The SAE or SUSAR Reporting Category, as defined in Version 2.0 of the DAIDS EAE Manual, will be used for this study.

The study products for which expedited reporting are required are:

- HIV-1gp120 (93MW965.26) DNA (Env-C Plasmid DNA)
- HIV Env gp145 C.6980 protein
- dmLT
- ALF43
- Rehydragel®

In addition to the SAE or SUSAR Reporting Category identified above, other adverse events that must be reported in an expedited manner are:

Potentially Immune-Mediated Medical Conditions (PIMMCs)

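### The three closing phone calls are meant to ask about medically attended adverse events, but the Section 5.5 list does not prompt for most kinds of medical visit or for non-serious immune-mediated diagnoses

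*Protocol*

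**What the plan says.** The Protocol Summary, under duration of individual participation, describes 105 weeks of clinic visits followed by "contact by phone once weekly for an additional three weeks to inquire about medically attended adverse events". The Precis, under study duration, repeats this: "Participants will be contacted by phone once weekly for an additional three weeks to inquire about medically attended adverse events".

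Section 5.5 is the only operational description of these calls. It says that "participants will be contacted once per week for 3 weeks (3 phone contacts) following the 105 week active study phase", and then "At these contacts, staff will collect the information listed below". After confirming vital status, staff are to "record the participant's responses to questions regarding any occurrence of the following events since the last study contact". The items are life-threatening experiences, persistent or significant disability, hospitalizations with reasons, a new HIV diagnosis, and pregnancies with outcomes. The term MAAE does not appear.

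Section 8.1.6 defines the target more widely: "MAAEs are defined as AEs with medically attended visits including hospital, emergency room, urgent care clinic", and continues with any other visit to or from medical personnel. It says that the FDA requests collection and analysis of MAAEs for 12 months or longer after the last vaccination, because adjuvants might in theory induce autoimmune or auto-inflammatory disease. Note 9 to Appendix A says that MAAEs are followed to the end of the study, for a full 12 months after the last dose.

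PIMMCs are to be recorded to the end of the trial (Section 7.2.2) and reported in an expedited manner (Section 8.2.1.1), over a reporting period of 108 weeks (Section 8.2.1.3).

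**The concern.** The stated purpose of the calls and the prescribed questions do not match. A site that works through the Section 5.5 list asks about serious outcomes, HIV and pregnancy. It does not ask whether the participant has seen a clinician or has been given a new diagnosis.

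At stake is the end of the long-term safety window for new adjuvant uses. Section 2.2.2 says that ALF43 has not been used in humans, and Section 2.2.3.5 says that this trial is the first to give dmLT by the transcutaneous route. After the 108-week reporting period, Section 8.2.1.3 provides only for SUSARs that staff learn of passively. A non-serious PIMMC diagnosed in weeks 106 to 108 and not volunteered has no later scheduled safety contact at which it would be picked up.

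**Working it through.** **Inputs.** Last vaccination: week 56, day 392 ± 7 (Appendix A). Exit visit: week 105, day 735 ± 14 (Appendix A). Calls: three, one per week after week 105 (Section 5.5). Participants: 126.

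**The plan's own figures.**
- End of participation: 105 + 3 = 108 weeks, as stated.
- Follow-up after the last dose: 108 − 56 = 52 weeks. In nominal days, 735 − 392 = 343 at exit, and 343 + 21 = 364 after the third call. The 12-month claim is reproduced, but only with the calls included.

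**How far the 12 months depends on the calls.**
- Without the calls: 105 − 56 = 49 weeks, or 343 days.
- Shortest interval to exit within the windows: (735 − 14) − (392 + 7) = 721 − 399 = 322 days.
- Longest: (735 + 14) − (392 − 7) = 749 − 385 = 364 days.
- The exit visit is therefore always short of 365 days when both visits are in window. The calls move the range to 343 to 385 days.
- Share of the window covered only by the calls: 3/52 = 5.8%.

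**Definition against list.**

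| Kind of event | Prompted by the Section 5.5 list? |
|---|---|
| Hospital visit | Yes, as hospitalization |
| Emergency-room visit | No |
| Urgent-care visit | No |
| Other visit to or from medical personnel | No |
| PIMMC that is fatal, life-threatening, disabling or hospitalized | Yes, through those items |
| Any other new PIMMC | No |

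One of the four MAAE visit types is prompted for.

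**Whether another part of the protocol fills the gap.** The Appendix A schedule has an MAAE row but ends at visit 26, week 105. Appendix G also ends at day 735. Neither has an entry for the calls. The script in Appendix Q is written for the call after a vaccination, with a diary-card reminder, and has no question about medical visits or new diagnoses.

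**What happens to an event once elicited.** Sections 8.1.3 and 8.1.8 say that, from 28 days after the last vaccination (week 56 + 4 = week 60), only SAEs and new chronic conditions needing ongoing management are entered in the database, through the last study visit. Other events stay in source documents. An acute, non-serious MAAE reported at a call would not reach the dataset. The rule does not say whether a phone contact after the exit visit counts as a study visit.

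**Illustration of scale, on an assumed rate.** The protocol gives no MAAE rate. At an assumed 0.2 to 2 MAAEs per person-year, with all 126 participants reached, the expected number in the three weeks is 126 × 0.2 × 3/52 = 1.5 to 126 × 2 × 3/52 = 14.5. These totals include hospitalized events, which the list does prompt for.

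**The case against.** The strongest reply is that the protocol must be read as a whole. Section 5.5 never says that staff may ask only the listed questions. The Summary and Precis still say that the calls ask about MAAEs, note 9 requires MAAE follow-up to study end, and Sections 7.2.2, 8.2.1.1 and 8.2.1.3 still oblige the site to record and report PIMMCs. Participants may volunteer events, and Section 5.5 allows a clinic visit to be arranged for other reasons. Clinic visits also cover MAAEs for 49 of the 52 weeks, and the primary endpoint does not name MAAEs.

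Much of this stands, and it rules out several stronger readings that a reader might infer:
- *That these events are missed, or that nothing is collected.* The documents show only that they are not prompted for. The duty to record them remains.
- *That the calls collect none of their target.* Hospitalizations are part of the MAAE definition and are asked about, as are life-threatening and disabling events.
- *That most PIMMCs would escape because they are diagnosed outside hospital.* Appendix O lists conditions and says nothing about where they are diagnosed, so the share affected cannot be stated.
- *That a zero count from the calls would mislead.* The plan sets no separate count or analysis for them.
- *That Appendix Q is a failed closing script.* It is optional guidance for another call, and it contains an open question about complaints. Its silence shows only that no closing-call script exists.

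The reply does not repair the list. A general duty to record an event does not make staff ask about it, and the only instruction on what to ask leaves out most of the stated purpose.

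**Conclusion.** The point holds as an internal inconsistency with a limited but real effect on late safety collection. For the last 3 of 52 weeks after the final vaccination, the prescribed questions prompt for one of four MAAE visit types and for PIMMCs only when they meet a serious-type item. Because in-schedule exit always falls short of 365 days, the full 12 months in note 9 depends on these calls. They are necessary for it and not always sufficient: at the short end of the windows the third call falls on day 343.

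This rests on three assumptions: visits occur within the Appendix A windows (out-of-window vaccination is possible at the PSRT's discretion), calls follow exit at 7-day steps, and sites work from the Section 5.5 list. How many events would go unreported is not known from the documents. Sample size, power and the primary tests do not change. It should be corrected, but it does not threaten the trial's main conclusions.

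**What to change.** 1. Add two items to the Section 5.5 list: any attendance since the last contact at a hospital, emergency room or urgent-care clinic, or with any other medical personnel; and any new diagnosis on the Appendix O list.
2. Provide a closing-call script with these questions, in Appendix Q or beside it. Entries for the three calls in Appendices A and G, with the MAAE row marked, would make the schedule agree.
3. Reconcile the data-entry rule in Sections 8.1.3 and 8.1.8 with Sections 7.2.2 and 8.1.6, so that MAAEs and PIMMCs elicited at the calls are entered in the database through week 108. Without this step, acute non-serious MAAEs found by the new questions would remain in source documents only.

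The cost is amendment text, two questions in each of at most 126 × 3 = 378 calls already planned, and the entry of any events reported. No visit, sample or analysis is added.

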5.6 OPTIONAL PROCEDURES

5.6.1 MUCOSAL COLLECTIONS

Participants will have the option of participating in separately consented mucosal collections. These collections will be conducted at the Kericho site at baseline and subsequent intervals per the SOE. Every effort will be made to have the procedures begin early, and in the event that this is not achieved, the procedures will be split and done over two consecutive days, within the study visit window.

5.6.1.1 Female Participants

Female participants may choose to undergo in cervicovaginal secretion and or rectal sponge secretion collections. Rectal secretions will be collected by rectal sponges by use of a rectal speculum and 2-4 sponges are inserted into the rectum mucosa for at least 4 minutes. The collected sponges will be placed in a sterile conical tube and shipped to the lab for processing. Consenting women will be instructed on how to use a Softcup device to collect cervicovaginal secretions. The cup will remain in place for 4-12 hours. Women that consent for cervicovaginal secretion collection will undergo a PAP smear test at screening. A urine pregnancy test will be done prior to each collection. Pregnant women and those with a history of toxic shock syndrome will be excluded. Date of last menstrual period will be recorded at each collection visit. The collection will not take place if the woman is menstruating or has symptoms of active inflammation or

infection of the vagina or cervix. Rectal sponge secretions will also be collected however will be deferred if there are signs or symptoms of perianal inflammation. Participants will be asked to refrain from penetrative sex up to 72 hours prior to Softcup or sponge placement.

5.6.1.2 Male Participants

Male participants may participate in semen collection and or rectal sponge secretion collections. Consenting men will be asked to ejaculate into a sterile container for semen collection. Rectal secretions will be collected by rectal sponges by use of a rectal speculum and 2-4 sponges are inserted into the rectum mucosa for at least 4 minutes. The collected sponges will be placed in a sterile conical tube and shipped to the lab for processing. Rectal sponge secretions will also be collected at this visit if the participant agrees. Semen and rectal sponge collections will be deferred from men if there are signs or symptoms of urethral or perianal inflammation, respectively. Participants may participate in semen collection and or rectal sponge secretion collections.

5.6.2 LYMPH NODE BIOPSIES

Excisional lymph node biopsies have been performed (for reasons other than sentinel node staging for cancer) by research sites around the world including MHRP sites in Kenya, Uganda, Tanzania, Thailand in HIV-infected and uninfected study participants, without any post-operative severe sequelae. Moreover, a recent article describing a meeting of experts discussed the importance of evaluating germinal center responses following immunization to predict broadly neutralizing antibody potency and breadth. A review of existing data showed that risks associated with excisional biopsies are low and with few complications [94].

Willing study participants will have the option of participating in a separately consented procedure of excision of intact inguinal lymph nodes. Inguinal lymph node excision will be offered at week 14 and week 58 and will be performed by a qualified doctor trained to perform superficial lymph node excision. The procedure will be performed under local anesthesia and last approximately 30-40 minutes. Anesthetics, antiseptics, and antibiotics are per surgeon's SOP and will be modified if the participant reports an allergy or sensitivity. Participants will then be asked to rest under observation for another 2-3 hours. Post-procedure, participants will return to the clinic in about 1 week for assessment of the biopsy site.

Coagulation testing will be done approximately 1 week before each biopsy and urine pregnancy testing will be done just prior to each biopsy.

Participants will be asked for their consent for photography if the clinician wishes to document an unusual or unexpected finding. Pictures may also be taken of the biopsy site immediately after the procedure and again 6 months later in order to provide an objective reference for biopsy site healing (i.e. for participant safety) and for possible use as participant educational material (for other participants who undergo the same procedure).

Assessment of the biopsy site includes:

- Evaluation for infection
- Seroma
- Cellulitis

- Lymphedema
- Pain
- Bleeding
- Hematoma
- Erythema
- Scarring
- Adhesive tape reaction
- Numbness or altered sensation of the area.

